#### **2.5 Correlative Studies Background**

Not Applicable

### 3. Study Design

#### 3.1 Overall Design

**Research question:** Can detectable levels of bowel gas methane (CH4) and/or hydrogen (H2) be detected in the abdominal cavity when the bowel is open during laparoscopic right colectomy with intracorporeal anastomosis using Perf-Alert™ detection system?

**Research Hypothesis: H1:** Bowel gas, methane (CH4) and/or hydrogen (H2) can be detected in the abdominal cavity when the bowel is open during laparoscopic right colectomy with intracorporeal anastomosis using the Perf-Alert™ detection system.

#### Design

Prospective pilot, single-center, single arm, open label, phase 1 investigator-initiated study to determine device ability to detect bowel gas during laparoscopic right colectomy with intracorporeal anastomosis using Perf-Alert™ gas detection system on 20 subjects into 2 Cohorts.

**Cohort 1:** 10 subjects with measurement of bowel gas at 8 predetermined time points during right laparoscopic colectomy as follow:

- 1) Initiation of surgery/laparoscopy start Insufflation
- 2) Abdominal exploration
- 3) Completion of colon mobilization
- 4) Colon transection
- 5) At Colotomy
- 6) At Enterotomy
- 7) Anastomosis completion
- 8) End of surgery- after re-insufflation before closure

**Cohort 2:** 10 subjects with continuous monitoring of bowel gases through the surgery. The level of H2 and CH4 gases will be noted at the 8 predetermined time points during the continuous monitoring as well.

#### 3.2 Scientific Rationale for Study Design

Preliminary investigation of a novel device to detect intraoperative bowel perforation/leak during right laparoscopic colectomy. The study will include a prospective quantitative assessment of intra-abdominal gaseous content during intracorporeal anastomosis procedures to determine the detectability of bowel gas or lack thereof when the bowel is intact and open. All study participants will be subject to the same protocol, and there will be no control group given the nature of the study and desired data. Each subject will be its own control using the baseline measurement as reference. For a phase one preliminary investigation, this design is appropriate because we cannot collect the study samples in a retrospective fashion, and the data from the prospective cohorts will provide the necessary information to test the study hypothesis and answer the research question.

#### 3.3 Justification for Dose

*Not Applicable*

### **3.4 End of Study Definition**

A clinical trial is considered completed when participants are no longer being examined or the last participant's last study visit has occurred. For this study it will be after subject 20 has completed the surgery.

A participant is considered to have completed the study if he or she has right laparoscopic colectomy with intracorporeal anastomosis completed.

## **4. Subject Selection**

### **4.1 Study Population**

Subjects who are undergoing right laparoscopic colectomy with intracorporeal anastomosis for regular care of their medical condition, and who meet the inclusion and exclusion criteria will be eligible for participation in this study.

### **4.2 Inclusion Criteria**

1. Male or female  $\geq$  18 years of age.
2. Documentation of a required elective right laparoscopic hemicolectomy with intracorporeal anastomosis
3. Subject signed informed consent

### **4.3 Exclusion Criteria**

1. Less than 18 years old
2. Pregnant or breastfeeding
3. Patients undergoing emergency laparotomy for perforated right colon or trauma
4. Patients with Intraabdominal abscess, peritonitis or enteric fistula
5. Patients who are on peritoneal dialysis
6. Subjects do not speak English

### **4.4 Lifestyle Considerations**

*Not applicable*

### **4.5 Screen Failures**

Screen failures are defined as participants who consent to participate in the clinical trial but are not subsequently randomly assigned to the study intervention or entered in the study. A minimal set of screen failure information is required to ensure transparent reporting of screen failure participants, to meet the Consolidated Standards of Reporting Trials (CONSORT) publishing requirements, and to respond to queries from regulatory authorities. Minimal information includes demography, screen failure details, eligibility criteria, and any serious adverse event (SAE).

In this study, subjects who have signed the consent but do not meet the inclusion and exclusion criteria listed in sections 4.2 and 4.3 will be considered screen failures.

#### **4.6 Strategies for Recruitment and Retention**

The potential subjects for this study will be identified from the practice of the Colon and Rectal Surgery, through screening of the daily schedule on EPIC. Subjects scheduled for right laparoscopic colectomy with intracorporeal anastomosis for regular treatment of their medical condition will be invited to participate in the study. The subjects willing to participate in the study will be presented with the research informed consent and introduced to the study. Subject understanding of the study will be assessed, and a full understanding of the study has to be demonstrated by the subject before they sign consent. The subjects will be recruited during the preoperative clinic visit or while in-patient

We are targeting to recruit 20 subjects, male and female, of all ethnic groups. No vulnerable populations will be included in the study. The current colorectal practice includes 8 surgeons, and with no competing study, we believe that we will be able to recruit these subjects for 12 months. The participants will not be compensated for their participation in the study. Also, there are no extra visits that have to be made due to the research study. All the procedures are standard of care, except the gas samples.

#### **5. Registration Procedures**

##### **5.1 Subject Registration (WCM only)**

Subjects will be registered within the WRG-CT as per the standard operating procedure for Subject Registration.

##### **5.2 Subject Registration (Sub-sites)**

*Not applicable*

#### **6. Study Procedures**

##### **6.1 Schedule of Assessments**

**Table 1. Schedule of trial events**

	Before Surgery	Day 0 Surgery	Post op In Hospital	30 ±2 days Follow Up
Informed consent	X			
Inclusion/ Exclusion	X			
Demographics	X			
Medical history	X			
Medication	X			
Intraoperative data		X		
Hydrogen H2 Samples		X		
Methane Samples CH4		X		
Anesthetic gases				

Post op data			X	X
--------------	--	--	---	---

#### 6.1.1 Screening Visit (30 days before start of treatment)

- *Informed consent*
- *Medical history*
- *Physical exam*
- *Medications*
- *Collect vital statistics – age, gender*

#### 6.1.2 Day of Surgery

- *Intraoperative data*
- *Hydrogen H2 Samples*
- *Methane CH4 Samples*
- *CO2 flow/rate*
- *Intraabdominal Pressure (mmHg)*
- *Anesthetic gases*
- *Total Volume CO2*

**Sample Collection Table**

Procedure Stage	Laparoscopy Start Insufflation	Abdominal Exploration	Completion of Colon mobilization	Colon transection	At Colotomy	At Enterotomy	After anastomosis completion	Re-Insufflation Before Closure
Sample #	S1_Baseline	S2	S3*	S4*	S5	S6	S7	S8
Time of collection								
H 2								
CH 4								
CO 2								
CO 2 flow/rate								
Intraabdominal Pressure (mmHg)								
Volume								
Re-Insufflation Y_N								

Anesthetic gases								

\*- Collect sample before smoke evacuation

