**1.1 Schema**

Prior to Enrollment

Total N: Obtain informed consent. Screen potential participants by inclusion and exclusion criteria; obtain history, vital stats (age, gender, height, weight, BMI) document.

Arm 1  
20 participants

Surgery Initiation Time Point

Connect Perf Alert™ to Operative Trocar Port  
Sterile tube/filter assembly to be opened in sterile field and affixed to accessible trocar port via standard leur connection ensuring air-tight seal. Surgeon or OR nurse will hand the other end of the tube to the Perf-Alert™ operator for connection.

Post Insufflation Time Point

Post insufflation but prior to initiation of surgical procedure, initiate **Sample Collection** as follows: 1. Open valve of trocar port to allow abdominal gas to pass through. 2. Open valve at Perf-Alert™ and initiate sample collection by turning on pump – let run for 60 seconds. 3. Close valve of trocar to stop the flow of gas from the abdomen.

Time points For Sample Collection

- 1) Initiation of surgery/laparoscopy start Insufflation
- 2) Abdominal exploration
- 3) Completion of colon mobilization
- 4) Colon transection
- 5) At Colotomy
- 6) At Enterotomy
- 7) Anastomosis completion
- 8) End of surgery- after re-insufflation before closure

End of Surgery Time Point

Prior to conclusion of surgery and removal of trocars, repeat Sample Collection procedure.

Post Operative

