## **10. Measurement of Effect**

### **10.1 Response Criteria**

Measurement of gastrointestinal gases (CH4 and/or H2) when the bowel is in an open condition will constitute a positive response for this study.

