### **12. Statistical Considerations**

## 12.1 Study Design/Endpoints

**Research question:** Can detectable levels of bowel gas methane (CH4) and/or hydrogen (H2) be detected in the abdominal cavity when the bowel is open during laparoscopic right colectomy with intracorporeal anastomosis using Perf-Alert™ detection system?

**Research Hypothesis: H1:** Bowel gas, methane (CH4) and/or hydrogen (H2) can be detected in the abdominal cavity when the bowel is open during laparoscopic right colectomy with intracorporeal anastomosis using the Perf-Alert™ detection system.

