### **13. Adverse Event Reporting Requirements**

This study will not report specific adverse events, as subjects are undergoing surgery for regular care. Furthermore, the device that will be used to collect and analyze the bowel gases from the abdominal cavity during surgery is not in direct contact with subjects and does add additional physical risk to the subjects. During laparoscopy, the abdominal cavity is being insufflated with carbon dioxide (CO2) gas, and a standard pressure between 12mm -15 mm/Hg is maintained throughout the surgery in the abdominal cavity for visualization through a CO2 insufflation tubing connected with one of the surgical trocars. If the pressure changes, for example, during instrument exchange through the laparoscopic port, the CO2 insufflator automatically starts the CO2 flow, so the pressure could be maintained between 12mm -15 mm/Hg. When a gas sample for the study is collected from the abdominal cavity, the insufflator will simultaneously replace any volume of gas removed with new CO2 gas. Therefore, there is no additional risk to the patient due to the gas sample collection for research during the surgery. All the intraoperative complications, should there be any, would be part of the regular surgical care risk.

However, all intraoperative complications will be collected as part of the study data collection. Also, to ensure safety, the intra-abdominal pressure level will be collected as a data point at the time of sample collection as part of the safety monitoring measure.

Any hydrogen (H2) and methane (CH4) detected by the device at time points when clinically, these gases are not expected to be found in the abdominal cavity, the operating surgeon will be notified.

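### The sample-before-smoke-evacuation rule stops at S4 and leaves out S5 (colotomy) and S6 (enterotomy), so bowel gas may be vented before those two draws, and the form would not show it

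*Combined protocol and SAP*

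**What the plan says.** The Sample Collection Table (Section 6.1.2) lists eight samples, S1 to S8. An asterisk refers to the footnote "Collect sample before smoke evacuation". From the third sample on, the labels read "S3* S4* S5 S6 S7 S8", so the rule is attached to S3 and S4 and to nothing later. The stages for S5 and S6 are "At Colotomy At Enterotomy".

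No other section mentions smoke evacuation. The general sampling steps in the Schema (Section 1.1) say to open the trocar valve, "initiate sample collection by turning on pump – let run for 60 seconds", and close the valve. They set no order between a draw and any venting of the cavity.

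H1 in Section 12.1 (also Section 3.1) is that CH4 and/or H2 "can be detected in the abdominal cavity when the bowel is open during laparoscopic right colectomy". Section 10.1 says that measuring either gas "when the bowel is in an open condition will constitute a positive response for this study". On gas exchange, Section 13 says that during a draw "the insufflator will simultaneously replace any volume of gas removed with new CO 2 gas".

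**The concern.** The trial asks whether the device can detect bowel gas once the bowel is open. Two of the eight stages are named for opening it, and at both the order of sampling and evacuation is left free. At S3, which comes before any planned opening, the order is fixed.

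If smoke is cleared after the bowel is opened but before the draw, part of the released gas leaves with it and CO2 takes its place. The resulting error runs one way, towards lower readings and missed detections. It also cannot be identified afterwards: a negative S5 or S6 could mean that the device failed to detect gas or that the gas had already been removed. A detectability pilot needs to tell these apart.

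**Working it through.** The plan gives no figure to reproduce, since the 20 subjects are not based on a power calculation (Section 12.2). The check is mainly of the text.

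**1. Which evacuations matter.** Taking colotomy before enterotomy, as the samples are numbered:

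| When smoke is evacuated | Effect | Excluded by the footnote? |
|---|---|---|
| After the S4 draw, before colotomy | Removes carry-over only; colotomy gas is not yet released | No, but it does not harm the target |
| After colotomy, before the S5 draw | Lowers S5 | No |
| After the S5 draw, before enterotomy | Removes colotomy gas that would otherwise contribute to S6 | No |
| After enterotomy, before the S6 draw | Lowers S6 | No |

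The second and fourth rows are the core of the point. The third affects S6 only.

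**2. Which comparisons are affected.** Section 3.2 makes each subject its own control against the baseline measurement, and the table labels S1 as baseline. The affected contrasts are therefore S5 versus S1 and S6 versus S1, together with the S5 and S6 detection frequencies. The exploratory pairwise tests in Section 12.4.1 that set S5 or S6 against S3 or S4 would also compare samples taken under different rules.

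**3. Whether the planned data would reveal it.** The form records collection time, CO2 flow/rate, pressure, volume and re-insufflation (Y/N) for each sample. These are indirect traces of gas exchange; none records smoke evacuation. Section 12.4.1 keeps the maximum value for each sample, but that is the maximum within the draw. In a spot sample it cannot recover a level that fell before the draw began.

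**4. Size.** For a per-sample detection rate, one lost detection is 1/10 = 10 percentage points within a cohort, or 1/20 = 5 points with the cohorts pooled.

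For the loss of concentration, the documents give neither the cavity volume nor the evacuated volume. As an illustration only, assume a well-mixed cavity of V = 3 to 5 L and no further gas release. The fraction remaining after venting E litres with CO2 replacement is exp(−E/V):

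| E vented | V = 3 L | V = 5 L |
|---|---|---|
| 0.5 L (the device's own draw, Section 13.1) | 0.846 | 0.905 |
| 1 L | 0.717 | 0.819 |
| 3 L | 0.368 | 0.549 |
| 5 L | 0.189 | 0.368 |

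This shows the direction, and that the effect need not be trivial. It is not an estimate. An open bowel may go on releasing gas, which would make the true loss smaller. Without a detection limit, no row converts into a number of missed detections.

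**The case against.** The strongest reply is that the footnote gives no reason for its scope. S3 and S4 may be marked simply because smoke is expected there, and a draw taken at colotomy or enterotomy may follow the opening so promptly that no evacuation intervenes. That stands as far as it goes: this is a missing instruction, not a stated practice of venting first. It does not close the gap, because nothing in the text excludes venting first.

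A reader might infer more than the documents support:

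- *That H1 rests wholly on unprotected samples.* The documents never list which samples count as bowel open. S4, colon transection, may be one, and it is covered. The response criterion has no per-sample rule, so a low S5 does not by itself lose a subject detected at S4 or S6. The 10-point step therefore applies to a per-sample rate, not necessarily to the subject-level response.
- *That a protected reference is set against unprotected samples.* The named reference is S1, not S3. Protection of S3 matters only for the exploratory pairwise comparisons.
- *That both cohorts are equally exposed.* Cohort 2 is monitored continuously and may show a peak before venting. The level noted at each time point is still exposed, but the main risk is in Cohort 1.
- *That the sponsor knew of the dilution and overlooked it.* The footnote does not state its purpose, so intent cannot be read from it.
- *That all eight samples should carry the rule.* S8 follows planned ex-sufflation and re-insufflation (Section 2.4.1), and a blanket rule would conflict with that.

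**Conclusion.** The point holds as a gap in the sampling instructions on the primary question. The plan permits smoke evacuation between bowel opening and the S5 or S6 draw, and for S6 also after an earlier colotomy. By the protocol's own account of CO2 replacement, this would lower the readings and bias S5/S6 detection and the contrasts with S1 towards non-detection, mainly in Cohort 1.

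The size cannot be stated, because the frequency of evacuation at these stages and the detection limit are both absent. The conclusion rests on the footnote meaning what its asterisks show and on evacuated gas being replaced by CO2 as sampled gas is. It does not rest on the illustrative volumes. The analyses are descriptive and exploratory, so no confirmatory claim is at risk. The change is still worth making before further cases, because whether smoke was evacuated before a draw cannot be reliably reconstructed after surgery.

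**What to change.** 1. Extend the existing asterisk to S5 and S6. Word it as a rule on when the sample is drawn, leaving surgical management to standard care (Section 7). Do not extend it to S8. If the restriction to S3 and S4 is deliberate, state the reason.
2. Add one row to the Sample Collection Table: *smoke evacuated between bowel opening or previous sample and this draw, Y/N*. The row is needed even with the wider asterisk, because evacuation after the S5 draw and before enterotomy would still be possible.
3. Add a sentence to Section 12.4.1 saying that S5 and S6 levels and detection frequencies will be shown with and without flagged samples.

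The cost is one form row and a footnote change. Any evacuation wanted at these two points would wait for the draw, within the 60 to 90 second pause that Section 2.4.3 already plans at each time point. If evacuation there proves rare, the row will document that.

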### 6.1.3 Follow-up Phase

Subjects will be followed postoperatively up to discharge from hospital and once again at 30 ±2 days after surgery. Relevant post-surgical complications will be collected.

## 7. Study Intervention

The anesthesia and the laparoscopic right colon surgery will be performed as per standard regular care.

### 7.1 Study Intervention/Device Description

The Perf-Alert™ device consists of a 15" x 13" x 7" unit containing gas sensors and valves, an ultra-low pressure pump, user controls (buttons), and software algorithms, which control the operation of the device. It is used in conjunction with a single-use, disposable kit consisting of sterile tubing and filters used for sample collection and transport. The sensing unit will be connected via a sterile tube/filter set to any trocar port in use during the procedure. At specific time points during the procedure, a one-way valve will be opened, and the unit's pump turned on is withdrawing small aliquots of gas from the abdominal cavity to the sensing unit. The system's architecture is configured such that sample collection, transport, analysis, and feedback occur in a single step such that sample collection and sensor feedback occur in real-time. A standard laptop running an analytical software program is connected to the unit to record and log sensor readings. The device will sit outside the sterile operative field and operated by a study coordinator with a representative of the device manufacturer present in the operating for troubleshooting.

### 7.2 Availability

*Perf-Alert™* is an investigational device supplied to investigators by Sentire Medical Systems, Inc. for the duration of the study

### 7.3 Acquisition and Accountability

Perf-ALert™ is an investigational device supplied to investigators by Sentire Medical Systems, Inc. for the duration of the study. The device will be stored at the research office located at K802C. The device will be examined by the Biomedical Engineering in the Greenberg Operating Rooms and will be approved for use in the operating room.

### **7.10 Duration of Follow Up**

Not applicable

### **7.11 Measures to Minimize Bias:**

This is a prospective pilot interventional, single-center, single-arm, open-label, phase 1 investigator-initiated study to determine device ability to detect bowel gas during laparoscopic right hemicolectomy with intracorporeal anastomosis using Perf-Alert™ gas detection system on 20 subjects into 2 Cohorts. To minimize the selection bias, we will enroll 20 consecutive subjects willing to participate in the study. The first 10 subjects will be part of Cohort 1, and the following 10 subjects will be part of Cohort 2.

### **7.12 Study Intervention/Follow-up Compliance**

Subjects will be followed up to 30 ±2 days after surgery

## **8. Study Intervention Discontinuation and Participant Discontinuation/Withdrawal**

### **8.1 Discontinuation of Study Intervention**

Any irregularity or complication during the surgery being performed will be grounds for discontinuation of the study intervention and withdrawal of the subject from the study. If the laparoscopic surgery has to be converted to an open surgical approach due to medical reasons or technical reasons, the study intervention will be discontinued and the subject withdrawn from the study.

No data will be collected at the time of study intervention discontinuation, and any data previously collected will be excluded from the study analysis and appropriately destroyed.

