### **8.2 Participant Discontinuation/Withdrawal from the Study**

Participants are free to withdraw from participation in the study at any time upon request. An investigator may discontinue or withdraw a participant from the study for the following reasons:

- If any clinical adverse event (AE), laboratory abnormality, or other medical condition or situation occurs such that continued participation in the study would not be in the best interest of the participant

The reason for participant discontinuation or withdrawal from the study will be recorded on the on the intraoperative Case Report Form (CRF) and reflected in the WCMC subject registration site. Subjects who sign the informed consent form but do not receive the study intervention may be replaced. Subjects who sign the informed consent form, and receive the study intervention, and subsequently withdraw, or are withdrawn or discontinued from the study will be replaced.

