**12.4 Analysis of Endpoints**

**12.4.1 Analysis of Primary Endpoints**

The gas sample gas composition will be analyzed automatically by the Perf-Alert™ gas detection system at the 8 different predetermined time points listed in 12.1. The measurements will be recorded in the data collection forms. The maximum value for the particular sample gases – H2 and CH4, will be recorded and included in the descriptive analysis.

Specifically, the presence of Hydrogen (H2) and Methane (CH4) gas measured in ppm or mg/L (parts per million or milligrams per liter (mg/L) at the 8 time points during the surgery will be descriptively assessed. Descriptive statistics (e.g., mean, standard deviation, median, interquartile range, frequency and percent) will be calculated for these parameters. Ninety-five percent confidence intervals will be calculated for all parameters of interest to assess the precision of the obtained estimates. No formal hypothesis testing will be performed in the pilot study. However, pairwise time point comparisons will be evaluated by the paired t-test or Wilcoxon signed-rank test, as appropriate. Due to the small sample size in this pilot study, all analyses will be considered exploratory and hypothesis-generating with no adjustment for multiple comparisons. All p-values will be two-sided with statistical significance evaluated at the 0.05 alpha level. All analyses will be

conducted using SPSS for Windows v.25 (IBM Corp. Released 2016. IBM SPSS Statistics for Windows, Version 24.0. Armonk, NY: IBM Corp).

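### Gas readings from subjects withdrawn for an irregularity, complication or conversion are dropped and destroyed and the subject replaced, so the analysed 20 are selected on events during the operation

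*Combined protocol and SAP*

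**What the plan says.** Section 8.1 has two triggers. For intraoperative events: "Any irregularity or complication during the surgery being performed will be grounds for discontinuation of the study intervention and withdrawal of the subject". For conversion to an open approach the wording is mandatory: "the study intervention will be discontinued and the subject withdrawn from the study". It then says "No data will be collected at the time of study intervention discontinuation", and of readings already taken that "any data previously collected will be excluded from the study analysis and appropriately destroyed".

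Section 8.2 adds that subjects who received the intervention "and subsequently withdraw, or are withdrawn or discontinued from the study will be replaced". It also says: "The reason for participant discontinuation or withdrawal from the study will be recorded", on the intraoperative case report form and in the registration system.

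On the outcome, Section 10.1 says that measuring CH4 and/or H2 "when the bowel is in an open condition will constitute a positive response for this study". Section 12.4.1 says: "Descriptive statistics (e.g., mean, standard deviation, median, interquartile range, frequency and percent) will be calculated for these parameters", and adds 95% confidence intervals. Neither 12.4.1 nor 12.4.2 defines an analysis set or a sensitivity analysis that would keep withdrawn subjects. Sections 7.11 and 12.2 describe the sample as 20 consecutive subjects, and 7.11 gives this as the means of limiting selection bias.

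**The concern.** Sampling starts at insufflation (Sections 3.1 and 6.1.2), so by the time an irregularity, complication or conversion occurs a subject may already have contributed readings. Whether those readings count then depends on later events. Irregularity is not defined, the study is open-label, and Section 7.1 says the device gives feedback in real time, so whoever applies the rule can know the readings. Consecutive enrolment does not protect against exclusions made after enrolment.

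The lost cases may be informative ones. A recognised bowel injury is a complication, so its readings could be destroyed, even where the injury was found because the surgeon had been told of unexpected gas under Section 13. An injury that nobody recognises does not trigger Section 8.1 and is unaffected.

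At stake is the meaning of the main descriptive result. A detection percentage would describe only subjects who were not withdrawn, yet could be read as describing a consecutive series.

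**Working it through.** **Consistency of the text.**

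- Sections 13, 13.1.3 and 15 say intraoperative complications are collected as study data. Section 8.1 destroys data already collected from a subject withdrawn because of one. This is a direct contradiction.
- Section 12.1 lists intraoperative complications as a covariate. Where Section 8.1 is applied, that covariate has little variation left.
- Section 11.2.5 has study data kept after completion. That cannot be met for readings destroyed earlier.
- Section 8.1 stops data collection at discontinuation, while Section 8.2 records the reason on the intraoperative form. The reason and the medical record survive; the gas readings do not.

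**The plan's own figure.** The sample size is 10 + 10 = 20 (Section 12.2). It is justified only by pilot status, with no withdrawal rate or precision target, so there is no derivation to reproduce.

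**Chance that the rule operates (assumed rates).** If each subject is withdrawn independently with probability w, the chance of at least one withdrawal before the 20th completer is 1 − (1 − w)^20:

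- w = 5%: 64%
- w = 10%: 88%
- w = 20%: 99%

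The expected number withdrawn is 20w/(1 − w), which gives 1.1, 2.2 and 5.0 respectively.

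**Effect on the detection percentage (assumed k).** Let x of the retained 20 be detections, and let k withdrawn subjects have had an open-bowel sample. Subjects withdrawn before the bowel was opened are not evaluable under Section 10.1 and are not counted. The percentage among all evaluable subjects lies between x/(20 + k) and (x + k)/(20 + k), a width of k/(20 + k):

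- k = 1: 1/21 = 4.8 points
- k = 2: 2/22 = 9.1 points
- k = 5: 5/25 = 20 points

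Exact (Clopper-Pearson) 95% intervals are in brackets:

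| Reported in the 20 | k | If none of the k was a detection | If all of the k were |
|---|---|---|---|
| 20/20 = 100% (83–100%) | 2 | 20/22 = 91% (71–99%) | 22/22 = 100% (85–100%) |
| 20/20 = 100% (83–100%) | 5 | 20/25 = 80% (59–93%) | 25/25 = 100% (86–100%) |
| 18/20 = 90% (68–99%) | 2 | 18/22 = 82% (60–95%) | 20/22 = 91% (71–99%) |
| 18/20 = 90% (68–99%) | 5 | 18/25 = 72% (51–88%) | 23/25 = 92% (74–99%) |

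The 18/20 rows show that the bias can go either way. Section 12.4.1 does not say whether the cohorts are pooled. If they are reported separately, one evaluable withdrawal in a cohort of 10 gives a width of 1/11 = 9.1 points.

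**The case against.** The case on the other side is about weight rather than about what the text says.

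- **No derived effect.** Every figure rests on an assumed k. The lower bounds suppose that no withdrawn subject was a detection, and k = 5 means one evaluable subject in five withdrawn. If nobody is withdrawn, nothing changes. Section 12.4.1 calls all analyses exploratory, and no success threshold depends on the percentage. All of this stands, and it limits what can be claimed about size.
- **A completers' design.** Section 3.4 defines completion as having the laparoscopic procedure with intracorporeal anastomosis completed, and Section 4.1 defines the population by that procedure. A completers' set is thus an arguable choice for conversions. It justifies neither destroying readings nor excluding a complicated case that was completed laparoscopically.
- **Weaker conflicts.** Consecutive may refer only to the order of enrolment. The retention rule applies after study completion. Because complications are only grounds for withdrawal, some subjects with complications may stay in, and no covariate-adjusted analysis is specified. The withdrawal reason may be seen as an administrative entry rather than study data. These points soften the supporting arguments but leave the contradiction with Sections 13, 13.1.3 and 15.
- **Peripheral injury scenario.** Inadvertent injury is not an endpoint; the study asks about gas when the bowel is opened as planned. That is fair, but planned open-bowel readings taken before a complication or conversion are destroyed too.
- **One summary only.** The illustration covers a binary percentage, whereas Section 12.1 gives the primary endpoint as gas levels at eight time points. No effect on means or paired comparisons has been shown, and the documents state no range of readings from which to bound one.

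**Conclusion.** The concern holds. Exclusion, destruction and replacement are all explicit, nothing in the analysis sections offsets them, and the result is selection on events after measurement began. The structural finding rests on the text alone. The widths of 4.8, 9.1 and 20 points for one, two and five evaluable withdrawals are illustrations under an assumed k, and neither the actual size nor the direction of bias can be obtained from the documents.

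It should be treated as a required change even in an exploratory pilot. A missing analysis can be added later, but a destroyed reading cannot be restored, and with 20 subjects each one counts.

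**What to change.** 1. In Section 8.1, remove the instruction to exclude and destroy. State that readings up to discontinuation are retained and analysed unless the subject withdraws permission.
2. In Section 12.4.1, set one denominator rule: each time point uses every subject sampled at it, and open-bowel detection uses every subject with an open-bowel sample, whether or not later withdrawn or replaced.
3. Report every subject started, with reasons for withdrawal and any replacement, in a flow chart.
4. Give the completers-only result alongside as a sensitivity analysis.
5. Reconcile Section 8.1, including its statement on data collection at discontinuation, with Sections 8.2, 11.2.5, 12.1, 13, 13.1.3 and 15.

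When study sampling should stop is a clinical matter and is not addressed here.

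The cost is a wording amendment with IRB approval. The consent pages were not available for this review; if they promise destruction, the consent form must change as well. Complications are already to be collected, so the added work is keeping readings and complication entries for the withdrawn subjects. The reported percentage may turn out less favourable.
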